To ensure that we capture as much suicide-related data as possible, we will utilize procedures that have been developed for current ongoing large-scale suicide prevention clinical trials led by [name] (RO1 MH101129) and [name] (U01 MH106660). We obtain releases of information from patients at study start to conduct chart reviews throughout the study covering the two major healthcare systems in RI (CNE and Lifespan) and their corresponding EDs and inpatient units. We also collect treatment utilization data via self-report (THI) during follow-up assessments, and, at that point, we can ask participants for releases of information to request discharge summaries from additional hospitals that the patient may report attending. Consistent with previous studies, we scrutinize all hospitalizations or ED visits with any of the following characteristics: evidence of self-injury, mental health concerns, ingestion/overdose, and traumatic injury. Staff then read the discharge summary to determine if there is any evidence of current or recent intentional self-harm ideation or behavior, including whether any injury is sustained. Staff also use carefully developed definitions of suicide ideation and suicide attempt (from C-SSRS criteria) to determine whether there is evidence of either event in the medical record.

If the patient dies, staff record the death and whether there was any evidence of intentional self-injury leading to the death. As we have done in previous studies, if we are unable to locate a participant at follow-up, we will state or national death registries to ascertain whether he/ she died, and if so, cause of death. Thus, suicide outcomes will be determined using all data collected during the study from all possible sources, including follow-up assessments (C-SSRS), b) hospital chart reviews, c) and community clinician reports. Data from all sources will be reviewed by two research team members for congruence. Note that we will obtain releases of information from patients at study start to conduct chart reviews throughout the study covering the two major healthcare systems in RI (CNE and Lifespan) and their corresponding EDs and inpatient units. Disagreements between raters will be reviewed and adjudicated by Drs. [name] (MPI) and [name] (Co-I). All reports will be classified using C-SSRS criteria. In a larger-scale clinical trial, our primary outcome will be a composite: a) suicide attempts or b) suicides.

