Potential Moderators. We have identified several potential moderators of CLASP effects in our previous research that we believe may also be relevant to the proposed project, which we will consider testing in future, larger-scale studies. The manuscript describing these results is currently in preparation. The following factors were found to moderate the effects of CLASP in the previous ED-SAFE study (U01 MH088278) and are also potentially relevant to LifePlans: marital status (CLASP more effective for those not married) and number of previous psychiatric hospitalizations (CLASP more effective for those with more hospitalizations). We will also consider whether recent suicide attempt status and lifetime suicide attempt status moderates outcome.

Treatment utilization. We have adapted a brief, structured Treatment History Interview (THI)²⁵ which allows us to collect information about other depression treatments such as inpatient hospitalization or psychotherapy, including any care that happens outside of the CNE system. We will combine this with information from the outpatient chart review (i.e., from the Providence Center) and inpatient chart review (from Butler Hospital) to gain a full picture of treatment utilization.

Clinical stakeholder interviews. Basic demographic information will be collected from all participants using a short self-report measure. These data will include age, gender, ethno-racial background, education level, duration of employment in current position, and duration of employment in the field. Participants will complete a 30-minute individual interview by telephone or videoconference. Prior to the interview, we will send participants a brief description of the video series and sample content. This interview will be scheduled at the participant's convenience and will be audio or video recorded. Stakeholder interview agendas will assess: a) barriers to patients' medication/appointment adherence, b) how the field can use a video intervention to support aftercare, c) challenges patients face upon return to the community post-discharge, d) challenges faced by clinicians/organizations treating individuals with suicidal thoughts and/or behaviors. Questions will be delivered in an open-ended format to allow participants to share their opinions.

Retention and Adherence

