Participants in Phase 1 who are chosen to be filmed to be part of the LifePlans videos will be re-consented immediately prior to the time when the raw footage will be shot. Participants will be informed that once the final product is completed and made available to study participants or patients via a web-hosting site on the internet, CNE will no longer have complete control over the video. After the raw footage is shot and edited, participants will have an opportunity to view any footage of them that may be used in the final LifePlans video. At that point, they may request that part or all of the footage not be used in the LifePlans videos, and we will respect their wishes and not use that footage. If participants wish for their videos to be withdrawn at a later date, i.e., after they are hosted on a website, we will make every effort to withdraw those videos from the website. However, in the consent process, we will make it clear that we cannot guarantee that the video has not been copied by an external party, as the copying could occur even though we will take available measures to prevent it.

D3. Data Safety Monitoring Plan

A. Data safety and storage.

Please see section D.2 above.

B. Data access.

Only study staff will have access to data. No confidential information may be released outside Butler Hospital without the express written consent of the study participants, unless mandatory for child and elder abuse and in situations in which the risk of suicide or homicide is imminent.

C. Educational training.

Date most recently revised 3/22/2022

Protocol Version 2.5

Please see section on training of research personnel above.

D. Adverse events and unexpected problems.

The MPIs and Co-Investigator [name] will be responsible for monitoring and reporting adverse events. They will meet with staff weekly to review any adverse events.

Definitions

Serious Adverse Events. An adverse event (AE) is any untoward medical occurrence in a subject during participation in the clinical study or with use of the experimental agent being studied. A serious adverse event (SAE) is one that meets one or more of the following criteria:

- Results in death
- Is life-threatening (places the subject at immediate risk of death from the event as it occurred; includes a suicide attempt or drug overdose)
- Results in inpatient hospitalization or prolongation of existing hospitalization
- Results in a persistent or significant disability or incapacity

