- Results in a congenital anomaly or birth defect

An important medical event that may not result in death, be life threatening, or require hospitalization may be considered an SAE when, based upon appropriate medical judgment, the event may jeopardize the subject and may require medical or surgical intervention to prevent one of the outcomes listed in this definition.

In this study, we will monitor and report on the following SAEs:

- Suicide behavior
- Inpatient hospitalizations that are:
 - Suicide-related or
 - Psychiatric in nature or
 - Due to substance use or overdose
- Death for any cause

Unanticipated Problems (UPs). The Office for Human Research Protections (OHRP) considers unanticipated problems involving risks to subjects or others to include, in general, any incident, experience, or outcome that meets **all** of the following criteria:

- Unexpected in terms of nature, severity, or frequency given (a) the research procedures that are described in the protocol-related documents, such as the IRB-approved research protocol and informed consent document; and (b) the characteristics of the subject population being studied;
- Related or possibly related to participation in the research (“possibly related” means there is a reasonable possibility that the incident, experience, or outcome may have been caused by the procedures involved in the research); and
- Suggests that the research places subjects or others at a greater risk of harm (including physical, psychological, economic, or social harm) than was previously known or recognized.

SAE Monitoring and Reporting

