Given that we are recruiting a hospitalized sample with suicide risk and possible substance use disorders, we expect serious adverse events to occur, including suicide attempts, non-suicidal drug overdoses, and psychiatric rehospitalizations,. However, given the nature of the study, it is unlikely that SAEs will be related to the study procedures. If any of these adverse events occur, or any other unanticipated problems are identified, the following procedure will be activated: the research staff member who observes or is notified of an adverse event (e.g., suicide attempt) will notify the MPIs or their designee immediately. All study staff will be educated on the definition of SAEs and UPs so that they may report them to the MPIs as soon as possible after becoming aware of the occurrence of an SAE or UP. We will systematically assess for adverse events throughout the course of the trial (for Phase 2 and 3) via patient interview (C-SSRS, THI) and chart review at Baseline, Month 1, and Month 6. In addition, if a patient reports one of the above SAEs at any time, we will record and review it. The MPIs or their designee will complete an Adverse Event Form for each event that will include a level of severity and determine attribution (intervention-related or not). Reporting timeframes will vary by SAE type. Please see the table below for more details.

Data type	Frequency of review	Reviewer
SAEs (expected OR unrelated, including psychiatric rehospitalizations and suicide attempts)	Per occurrence	MPIs (within 72 hours) Reported to SMC in bi-annual reports Reported to NIH in annual progress reports
SAEs (related)	Per occurrence	MPIs (within 72 hours) Reported to IRB and SMC within 10 days Reported to NIH in annual progress reports
All deaths	Per Occurrence	MPIs (within 72 hours) Reported to IRB, SMC, NIH within 5 days
UPs	Per Occurrence	MPIs (within 72 hours) Reported to IRB and SMC within 10 days Reported to NIH in annual progress reports

Interim Analysis and Stopping Rules

There is no interim analysis planned.

This study will be stopped prior to its completion if: (1) the intervention is associated with adverse effects that call into question the safety of the intervention; (2) difficulty in study recruitment or retention will significantly impact the ability to evaluate the study endpoints; (3) any new information becomes available during the trial that necessitates stopping the trial; or (4) other situations occur that might warrant stopping the trial.

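### The study's list of SAEs to monitor and report omits non-fatal, non-suicidal drug overdoses that do not lead to admission, although the plan elsewhere treats them as SAEs

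*Combined protocol and SAP*

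**What the plan says.** Four places in the combined protocol and SAP bear on this.

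- **D3, part D, Definitions (general SAE criteria).** The life-threatening criterion "includes a suicide attempt or drug overdose". It sets no condition on intent or admission.
- **D3, part D, Definitions (study-specific list).** The list opens "In this study, we will monitor and report on the following SAEs" and has three entries: suicide behavior, certain hospitalizations, and death from any cause. The hospitalization entry begins "Inpatient hospitalizations that are" and has three sub-entries: suicide-related, psychiatric, and "Due to substance use or overdose". Overdose appears nowhere else on the list.
- **SAE Monitoring and Reporting.** The section opens by saying "we expect serious adverse events to occur, including suicide attempts, non-suicidal drug overdoses, and psychiatric rehospitalizations". If any of these occurs, staff are to notify the principal investigators at once, and an Adverse Event Form is completed for each event. The table row for expected or unrelated SAEs sends them to the Safety Monitoring Committee (SMC) in its twice-yearly reports and to NIH annually. That row gives rehospitalizations and suicide attempts as examples. It does not mention overdose and does not require admission.
- **C2, Suicidal Behaviors.** Chart review picks out hospitalizations and ED visits with "evidence of self-injury, mental health concerns, ingestion/overdose, and traumatic injury". Staff then read the discharge summary for signs of intentional self-harm.

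**The concern.** The general definition puts suicide attempt and drug overdose side by side. The study list then treats them differently: suicide behavior counts with or without admission, while a non-fatal overdose judged non-suicidal counts only if the participant is admitted. No reason is given. For an overdose treated in the ED and sent home, or never treated, its place on the list therefore turns on a judgement of intent.

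Staff are to be trained on what an SAE is, but the plan gives them two versions. The rule for events that a participant reports between assessments refers back to the SAEs above without saying which version it means.

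At stake is whether the same kind of event is recorded for one participant and not for another, and so whether the safety record can be read consistently across the two arms. Safety is one of the things that the section on potential benefits says the project will assess, and the sponsor itself expects this event in the population.

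**Working it through.** The plan states no figure on this point, so the check is a comparison of the texts. Sorting overdoses by outcome, intent and admission gives four groups:

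| Overdose | SAE by the general definition | On the study list | Within SAE Monitoring and Reporting |
|---|---|---|---|
| Fatal, any intent | Yes | Yes, as a death | Yes, table row for all deaths |
| Non-fatal, suicidal | Yes | Yes, as suicide behavior | Yes, suicide attempts are named |
| Non-fatal, non-suicidal, admitted | Yes | Yes, as a hospitalization | Yes, named |
| Non-fatal, non-suicidal, not admitted | Yes | **No** | Yes, named with no admission condition |

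Only the last group is affected.

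The next question is whether the stated ways of finding events settle what happens to that group.

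1. *Chart review.* SAE Monitoring and Reporting makes it a source of adverse events, and the Suicidal Behaviors section shows that ED visits for ingestion or overdose are already pulled. The step described after that is a search for intentional self-harm. Nothing says what is done with the visit when none is found.
2. *C-SSRS interview.* It is described as covering suicidal ideation, intent, plans and behavior. A non-suicidal overdose lies outside that description.
3. *Treatment History Interview (THI).* It is said to "collect information about other depression treatments such as inpatient hospitalization or psychotherapy", including care outside the hospital's own system, so it may bring an ED visit to light. Its items are not in the documents, so whether it asks about overdose cannot be determined.

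The sources can therefore bring many of these events to the team's notice. What is unsettled is whether an event, once known, is to be logged as an SAE.

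On size, the documents give no rate for overdoses of this kind, so no expected number can be derived. For scale only: 40 participants randomized 1:1 is about 20 per arm, so one participant whose only SAE was such an overdose changes that arm's proportion with any SAE by 1/20 = 5 percentage points. This does not say how often it would happen.

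**The case against.** The strongest reply is that SAE Monitoring and Reporting already covers these events. Its opening sentence names non-suicidal overdoses without requiring admission, the procedure is triggered by any of the events so named, a form is completed for each, and the table row for expected or unrelated SAEs has no admission condition. The investigators also review adverse events with staff weekly. The reference to the SAEs above can be read as pointing to that same opening sentence. And where intent decides classification, the Suicidal Behaviors section provides for two-person review, C-SSRS criteria and adjudication of disagreements.

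Most of this stands. A reader might infer that treated-and-released overdoses will drop out of the safety record; the documents do not support that, because staff who follow SAE Monitoring and Reporting would record them. The reply does not remove the conflict, however. The study-specific list is the one place that states outright what this study monitors and reports, and neither text says which one governs. A careful intent review also does not help an event that is correctly judged non-suicidal and is then not on the list.

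Three further inferences are tempting and should not be drawn. The number of lost events cannot be stated: it would need an overdose rate that the documents do not give, and the assumption that every such event is missed. The SMC cannot be said to apply the first stopping rule to an incomplete count, because the plan does not assign that rule to the SMC, and the rule concerns adverse effects associated with the intervention, not an SAE tally. Nor can the THI be said to lack an overdose question, since the instrument is not reproduced.

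**Conclusion.** The inconsistency is real and narrow. The study list omits non-fatal, non-suicidal overdoses without admission, while the general definition and the reporting section both treat them as SAEs. Depending on which text staff follow, such an event is either left out or recorded, so the safety record may be incomplete or uneven. The conclusion rests on the wording alone and needs no assumed event rate. The correction is worth making because the sponsor expects the event, safety is a stated aim and the change is small.

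**What to change.** Reconcile the general SAE definition, the study-specific list, and SAE Monitoring and Reporting:

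- Add a separate line to the study-specific list for drug overdose, whatever the intent and whether or not the participant is admitted.
- State that ED visits already flagged for ingestion or overdose under Suicidal Behaviors are entered on the Adverse Event Form even when no self-harm intent is found.

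If the narrower list was intended, the plan should say so, give the reason, and bring SAE Monitoring and Reporting into line with it.

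The cost is one line in the list and one sentence on chart review. The ED records are already being read. The downside is a few more forms and a slightly higher reported SAE count.

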Chart reviews of new patients will be routinely conducted by study staff to determine if they are likely to meet inclusion/exclusions criteria for the study as described above. PHI to be obtained: patient demographic and contact information (name, address, telephone numbers, gender, age, race, marital status, occupation status) and patient psychiatric/treatment history (diagnoses and suicide history, past and current psychological and/or pharmacological treatments, current mental health provider contact information, lab results).

7) ADVERTISEMENTS

Document attached.

8) INFORMED CONSENT FORM (ICF), ASSENT OF MINOR & PARENTAL PERMISSION FORM

Indicate number of consent(s): 9

Identify each consent (i.e., Main, Screening, DNA):

- Verbal Consent for email and videorecording prior to enrollment
- Phase 1A – Written consent
- Phase 1A-- Verbal consent
- Phase 1B- Consent for use of videos in LifePlans intervention
- Phase 1B – HIPAA release; media release; materials release; COVID risk acknowledgment
- Phase 2 – Main - Written consent
- Phase 2 – Stakeholders – Written consent
- Phase 3 – Written consent
- Phase 3 – Email/Videoconferencing verbal consent
